6.12.4. Other Secondary and Exploratory Efficacy Analyses

Other secondary and exploratory efficacy measures will use the efficacy estimand and will be summarized by treatment and nominal visit. Unless otherwise specified, missing data will not be

explicitly imputed, and assessments are not subject to type 1 error rate control. Some parameters may be log transformed, if necessary. Biomarkers analyses are to be determined.

Table GPGI.6.2. Secondary and Exploratory Efficacy Analyses Not Controlled for Type I Error

Objective	Relative to the efficacy measure:	Analysis Conducted in a manner similar to section:	Additional Information
Secondary Analyses			
To compare QW tirzepatide 5 mg, 10 mg, and 15 mg to placebo at 40 weeks in:	Proportion of patients achieving an HbA1c target value of $\leq 6.5\%$ (48 mmol/mol)	6.12.2.2	None
	Change from baseline in 7-point self-monitored blood glucose (SMBG) profiles	6.12.1.2	Use baseline HbA1c category as a fixed effect in place of baseline HbA1c as a covariate. Use baseline SMBG parameter as a covariate. LSM estimates at 40-weeks will be summarized by treatment and 7-points. In addition to the analyses on each of the 7-points, similar analyses will be done for the 2-hour morning, midday, and evening meal excursions, the mean of all meals 2-hour excursion, the mean of all 7-point measurements, the mean of all pre-meal measurements, and the mean of all 2-hour postprandial measurements.
	Proportion of patients who achieved weight loss of $\geq 5\%$, from baseline	6.12.2.2	Use baseline HbA1c category as a fixed effect in place of baseline HbA1c as a covariate. Use baseline weight as a covariate

Secondary and Exploratory Efficacy Analyses Not Controlled for Type I Error

Objective	Relative to the efficacy measure:	Analysis Conducted in a manner similar to section:	Additional Information
	Proportion of patients who achieved weight loss of $\geq 10\%$ from baseline	6.12.2.2	Use baseline HbA1c category as a fixed effect in place of baseline HbA1c as a covariate. Use baseline weight as a covariate
	Proportion of patients who achieved weight loss of $\geq 15\%$ from baseline	6.12.2.2	Use baseline HbA1c category as a fixed effect in place of baseline HbA1c as a covariate. Use baseline weight as a covariate
	Change from baseline in daily mean insulin glargine dose	6.12.1.1	Use baseline HbA1c category as a fixed effect in place of baseline HbA1c as a covariate. Use baseline insulin glargine dose as a covariate.
To compare QW tirzepatide 5 mg to placebo at 40 weeks in:	Proportion of patients achieving an HbA1c target value of $< 5.7\%$ (39 mmol/mol)	6.12.2.2	None
Exploratory Objectives			
To compare QW tirzepatide 5 mg, 10 mg, and 15 mg to placebo at 40 weeks in:	Change from baseline in lipid parameters (Total-Cholesterol, HDL-C, LDL-C, VLDL-C, TG)	6.12.1.2	Use baseline HbA1c category as a fixed effect in place of baseline HbA1c as a covariate. Use corresponding baseline lipid parameter as a covariate
	Change from baseline in waist circumference	6.12.1.1	Use baseline HbA1c category as a fixed effect in place of baseline HbA1c as a covariate. Use baseline waist circumference as a covariate
	Change from baseline in BMI	6.12.1.1	Use baseline HbA1c category as a fixed effect in place of baseline HbA1c as a covariate. Use baseline BMI as a covariate
	Change from baseline in patient reported outcomes: APPADL, IW-SP, EQ-5D-5L	6.12.1.2	Use baseline HbA1c category as a fixed effect in place of baseline HbA1c as a covariate. Use corresponding baseline patient outcome score as a covariate.

Secondary and Exploratory Efficacy Analyses Not Controlled for Type I Error

Objective	Relative to the efficacy measure:	Analysis Conducted in a manner similar to section:	Additional Information
	Patient reported DTSQc score	6.12.1.2	Use baseline HbA1c category as a fixed effect in place of baseline HbA1c as a covariate. Use DTSQs baseline patient outcome score as a covariate
	Proportion of patients achieving an FSG <100 mg/dL (5.5 mmol/L)	6.12.2.2	Use baseline HbA1c category as a fixed effect in place of baseline HbA1c as a covariate. Use baseline FSG as a covariate.
	Proportion of patients achieving an FSG <126 mg/dL (7 mmol/L)	6.12.2.2	Use baseline HbA1c category as a fixed effect in place of baseline HbA1c as a covariate. Use baseline FSG as a covariate.
To compare QW tirzepatide 5 mg, 10 mg, and 15 mg to placebo at 40 weeks in:	Proportion of patients achieving an HbA1c target $\leq 6.5\%$, without weight gain (<0.1 kg), and without documented symptomatic hypoglycemia or severe hypoglycemia	6.12.2.2	Include baseline body weight as an additional covariate
	Proportion of patients achieving an HbA1c target <7.0% without weight gain (<0.1 kg), and without documented symptomatic hypoglycemia or severe hypoglycemia	6.12.2.2	Include baseline body weight as an additional covariate
	Proportion of patients achieving an HbA1c target $\leq 6.5\%$ without weight gain (<0.1 kg), and without clinically significant documented symptomatic hypoglycemia or severe hypoglycemia	6.12.2.2	Include baseline body weight as an additional covariate
	Proportion of patients achieving an HbA1c target <7.0% without weight gain (<0.1 kg), and without clinically significant documented symptomatic hypoglycemia or severe hypoglycemia	6.12.2.2	Include baseline body weight as an additional covariate

Secondary and Exploratory Efficacy Analyses Not Controlled for Type I Error

Abbreviations: APPADL = Ability to Perform Physical Activities of Daily Living; BMI = body mass index; DTSQc = Diabetes Treatment Satisfaction Questionnaire change; DTSQs = Diabetes Treatment Satisfaction Questionnaire change; FSG = fasting serum glucose; HbA1c = hemoglobin A1c; HDL-C = high-density lipoprotein-cholesterol; IW-SP = Impact of Weight on Self-Perceptions Questionnaire; LDL-C = low-density lipoprotein cholesterol; LSM = least squares mean; QW = once-weekly; TG = triglyceride; VLDL-C = very-low density lipoprotein-cholesterol.

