9.2.2.2. Severe, Persistent Hyperglycemia

Severe, persistent hyperglycemia will be collected during the trial to assess the risk of extreme imbalance in glycemic control.

Investigators will be trained on the application of criteria for deciding when and how to intervene with patients who do not reach glycemic targets. An additional therapeutic intervention should be considered in patients who develop severe, persistent hyperglycemia after randomization at the discretion of investigator in accordance with American Diabetes Association/European Association for the Study of Diabetes guidance (Inzucchi et al. 2015). Rescue medication will be prescribed as add-on to randomized treatment, and patients will continue to follow the protocol-specified visit schedule.

Because insulin glargine dose adjustments without restrictions will be initiated at the end of the stabilization period (see Section 5.1), decision on the presence of severe, persistent hyperglycemia can be first considered 12 weeks after the initiation of this period (approximately 16 weeks after randomization)...

Add-on glycemic rescue therapy will be allowed for patients who met any one of the following prespecified criteria for severe, persistent hyperglycemia and no intercurrent cause of the hyperglycemia could be identified (investigators should first confirm that the patient is fully compliant with the assigned therapeutic regimen and that the patient does not have an acute condition causing severe hyperglycemia):

- (a) average daily BG from the once-weekly 4-point SMBG profile >270 mg/dL (>15.0 mmol/L) over at least a consecutive 2-week period at any time 16 to 24 weeks post randomization;

 OR
- (b) average daily BG from the once-weekly 4-point SMBG profile >240 mg/dL (>13.3 mmol/L) over a consecutive 2-week period at any time 25 to 32 weeks post randomization;

 OR
- (c) average daily BG from the once-weekly 4-point SMBG profile >200 mg/dL (>11.1 mmol/L) over a consecutive 2-week period at any time beyond the first 32 weeks post randomization.

 OR
- (d) HbA1c ≥8.5% at 24 weeks, with inadequate response to the existing regimen defined as improvement in HbA1c over the last 3 months (Week 12 to Week 24) that is, <0.3%

Rescue therapy option:

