6.1. Populations for Analyses

For purposes of analysis, [Table GPGI.6.1](#) defines analysis populations/data sets.

Table GPGI.6.1. Analysis Populations/Data Sets

Population/Data Set	Description
Screened population	All participants who sign informed consent
Randomized population	All patients who are randomly assigned a treatment arm
Modified intention-to-treat (mITT) population	All randomly assigned participants who are exposed to at least 1 dose of study drug. In the event of a treatment error, participants will be analyzed according to the treatment they were randomized.
Efficacy analysis set (EAS)	Data obtained during Study Period II from the mITT population, excluding patients discontinuing study drug due to inadvertent enrollment and data after initiating rescue antihyperglycemic medication or early discontinuation of study drug (last dose date + 7 days).
Full analysis set (FAS)	All available data obtained during Study Period II from the mITT population, regardless of adherence to study drug or initiation of rescue antihyperglycemic medication. Patients who discontinued study drug due to inadvertent enrollment will be excluded.
Safety analysis set (SS)	All available data obtained during Study Periods II and III from the mITT population, regardless of adherence to study drug or initiation of new antihyperglycemic medication.

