6.2. General Considerations

Statistical analysis of this study will be the responsibility of Eli Lilly and Company (Lilly) or its designee. All statistical analyses will be conducted with SAS Version 9.4 or higher unless otherwise stated. Any change to the data analysis methods described in the protocol will require an amendment only if it changes a principal feature of the protocol. Any other changes to the data analysis methods described in the protocol, and the justification for making the change, will be described in the SAP or the clinical study report (CSR). Some analyses and summaries described in this analysis plan may not be conducted if not warranted by data (e.g., few events to justify conducting an analysis). Listings of events will be provided in such situations. Additional analyses of the data may be conducted as deemed appropriate without further changes made to the protocol or SAP, even after the primary or final database locks (DBL).

Additionally, to avoid potential selection biases, unless stated otherwise, statistical summaries and analyses will be conducted based on randomized maintenance dose regardless of the actual treatment received by the patient.

Unless specified otherwise, the last measurement during Visit 1 to Visit 3 (including unscheduled visits) collected prior to or on the first dose day will serve as baseline.

- For immunogenicity, data collected up to the first dose time will serve as baseline.
- For lab and ECG, baseline needs to be prior to or within one hour after the first dose time.
- For patient-reported outcomes, data collected at Visit 3, regardless of the timing relative to first dose, will serve as baseline.

There will be 2 estimands of interest in evaluating the primary and secondary efficacy objectives. The first estimand, the “efficacy” estimand, represents efficacy prior to discontinuation of study drug without the confounding effects of rescue therapy for severe persistent hyperglycemia. Analyses relative to the “efficacy” estimand will be conducted using the efficacy analysis set (EAS). The second estimand, the “treatment-regimen” estimand, represents the efficacy irrespective of adherence to investigational product or introduction of rescue therapy for severe persistent hyperglycemia. Analyses relative to the “treatment-regimen” estimand will be conducted using the full analysis set (FAS).

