6.12.1.2. Primary Analysis Relative to the Treatment-Regimen Estimand

The primary analysis relative to the treatment-regimen estimand will be conducted utilizing HbA1c data in the FAS at baseline and at the 40-week visit with the aid of an ANCOVA model.

The response variable will be the primary measure and model terms will include treatment, country/pooled country, and baseline metformin use (Yes/No) as fixed effects and baseline HbA1c as a covariate. The ANCOVA analysis will be conducted using multiple imputation of missing primary measures (see Section 6.12.1.3 for details) and statistical inference over multiple imputation of missing data guided by Rubin (1987).

With the aid of the ANCOVA analysis, p-values and 2-sided 95% CIs for mean change in HbA1c from baseline to the 40-week visit will be derived and summarized for the 5 mg, 10 mg, and 15 mg doses of tirzepatide compared to placebo.

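### The 7-point SMBG row of Table GPGI.6.2 cites the treatment-regimen section; on its likeliest reading it is an unimputed on-drug completer comparison that loses patients rescued for high SMBG

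*SAP*

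**What the plan says.** SAP 6.12.4 sets a general rule for these endpoints: "Other secondary and exploratory efficacy measures will use the efficacy estimand and will be summarized by treatment and nominal visit". It adds that missing values are not explicitly imputed unless otherwise specified, and SAP 6.4 repeats this for every endpoint that is neither primary nor key secondary. SAP 6.2 ties the efficacy estimand to the EAS and says that it "represents efficacy prior to discontinuation of study drug without the confounding effects of rescue therapy for severe persistent hyperglycemia". Table GPGI.6.1 removes from the EAS any "data after initiating rescue antihyperglycemic medication or early discontinuation of study drug (last dose date + 7 days").

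Table GPGI.6.2 then gives each measure a section to be followed in a similar manner. For "Change from baseline in 7-point self-monitored blood glucose (SMBG) profiles" and for "Change from baseline in lipid parameters (Total-Cholesterol, HDL-C, LDL-C, VLDL-C, TG") that section is 6.12.1.2. This is the primary analysis for the treatment-regimen estimand. It uses "HbA1c data in the FAS at baseline and at the 40-week visit with the aid of an ANCOVA model", with multiple imputation of missing values.

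Protocol 5.1 and the Schedule of Activities place the 7-point profiles only in the two weeks before Visit 3 and before Visit 22. Protocol 9.2.2.2 defines rescue criteria (a) to (c) on SMBG. Criterion (b), for example, is an "average daily BG from the once-weekly 4-point SMBG profile >240 mg/dL (>13.3 mmol/L) over a consecutive 2-week period" in Weeks 25 to 32. Criterion (d) is based on HbA1c. Under Protocol 5.1, rescued patients stay on the visit schedule.

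**The concern.** Two things are unsatisfactory. First, the general rule and the row's cross-reference differ on both the data set and the treatment of missing values, and the row does not say which parts of 6.12.1.2 carry over.

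Second, the likeliest resolution (ANCOVA at Week 40, EAS, no imputation) does not deliver the efficacy estimand. With one post-baseline profile, a patient rescued or off drug before Week 40 contributes nothing, and the ANCOVA adjusts only for baseline factors. Removal through criteria (a) to (c) depends on average daily glucose, which is essentially what the endpoint compares. If the placebo arm loses more of its worst-controlled patients this way, its mean looks better than it should and the tirzepatide effect on SMBG is understated. The stake is how this secondary endpoint is interpreted.

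**Working it through.** **The plan's own figure.** The documents give no sample size or SD for SMBG. For HbA1c (SAP 5.2: difference 0.6, SD 1.1, two-sided 0.025, 90% power), n = 2 × (2.241 + 1.282)² × (1.1/0.6)² = 83.4, so 84 per arm. Dividing by 1 − 0.28 gives 117 per arm, or 468 in total. The planned 118 per arm leaves 118 × 0.72 ≈ 85 evaluable, and an exact t calculation gives 90.1% power. The planned 472 therefore reproduces. The present point does not rest on it.

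**How many could be lost.** At the plan's 28% ceiling for rescue and discontinuation combined, 0.28 × 118 ≈ 33 patients per arm (about 132 of 472) have no usable Week-40 SMBG value on the EAS. This is a ceiling, not a rescue rate.

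**Settling the reading.** Rows with several on-treatment visits (insulin dose, waist, BMI) cite 6.12.1.1, the MMRM. SMBG, lipids and the patient-reported outcomes, each with one planned on-treatment post-baseline value, cite 6.12.1.2. SAP 6.14 says the patient-reported outcomes are analysed by ANCOVA on the EAS, with the FAS as sensitivity. So the citation most plausibly borrows the model form only.

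**Size of the bias (assumptions).** Standardised effect taken from HbA1c: 0.6/1.1 = 0.545 SD. Rescue removes the fraction *r* with the highest pre-rescue value, using one threshold in all arms. The correlation of that value with Week 40, given baseline, is ρ. The retained mean then falls by ρ × m(r), with m(r) = φ(z)/(1 − r) and z the upper *r* quantile. The active arm's rescue rate is the tail beyond z + 0.545.

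| Placebo rescue | z | m (placebo) | Active rescue | m (active) | Difference in m |
|---|---|---|---|---|---|
| 5% | 1.645 | 0.1031/0.95 = 0.109 | 1.4% | 0.0362/0.986 = 0.037 | 0.072 |
| 10% | 1.282 | 0.1755/0.90 = 0.195 | 3.4% | 0.0752/0.966 = 0.078 | 0.117 |

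Attenuation = ρ × difference / 0.545:

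| Placebo rescue | ρ = 0.3 | ρ = 0.5 | ρ = 0.7 |
|---|---|---|---|
| 5% | 4% | 7% | 9% |
| 10% | 6% | 11% | 15% |

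Simulation with 118 per arm, a Week-24 trigger and ρ of 0.5 to 0.7, with unrelated discontinuation added, gave 6–8% and 10–14%. A separate simulation with equal loss in both arms (28% and 28%) by the same mechanism gave a shift of about zero.

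**Later rescue.** Criteria (b) and (c) act from Week 25, nearer the endpoint, so ρ is likely to be higher. At ρ = 0.85 the formula gives 0.85 × 0.072/0.545 = 11% and 0.85 × 0.117/0.545 = 18%.

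**What imputation can recover.** HbA1c and FSG have no on-treatment visit between Weeks 24 and 40. Simulating rescue near Week 34, imputation from Week-24 HbA1c removed only about 15–30% of the bias.

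**The case against.** The strongest reply is that nothing is really contradictory. SAP 6.12.4, 6.2 and 6.4 already fix estimand, data set and imputation rule; the table asks only for a similar manner; and SAP 6.14 shows how that is meant. This largely stands. A reader might infer that SMBG will actually be analysed on the FAS under the wrong estimand label, but the documents make that reading weak. What remains is a row that should say so, and settling it leaves the completer problem untouched.

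Second, the size is assumed. Rescue needs sustained high values, starts only at about Week 16, requires confirmed compliance, and is left to investigator judgement. Placebo rescue of 15–20%, at which larger attenuation can be computed, has no anchor in the documents. The standard error with 85 per arm is √(2/85) ≈ 0.15 SD, while 15% attenuation is 0.15 × 0.545 ≈ 0.08 SD. This stands, so only the range at 5–10% rescue is given, as an illustration.

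Third, the direction is conditional. Stopping tirzepatide for gastrointestinal intolerance could select patients differently, and equal loss for equal reasons gives no bias. This also stands.

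Fourth, the rescue trigger uses 4-point profiles, and criterion (d) uses HbA1c. That weakens the link but does not break it, since the 4-point and 7-point averages both measure daily mean glucose.

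**Conclusion.** The point holds as a specification gap plus informative exclusion for one secondary endpoint. On the likeliest reading, the SMBG comparison is among patients still on drug and unrescued at Week 40, and exclusion depends partly on the quantity compared. If rescue is more frequent on placebo, the tirzepatide effect is understated, by roughly 5–15% at 5–10% placebo rescue for a trigger around Week 24. This assumes the HbA1c standardised effect, a common threshold and correlations of about 0.3 to 0.7. Rescue closer to Week 40 could push it somewhat higher, and it is near zero if rates and reasons match across arms.

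Three further inferences are not supported. The primary and key secondary conclusions are not affected: SMBG is outside type 1 error control. No bias is shown for lipids, because rescue is not triggered by lipid values; their defect is only the unresolved cross-reference. And the HbA1c and FSG MMRMs should not be held up as free of the problem: they use earlier on-drug visits, but have none between Weeks 24 and 40.

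**What to change.** In the SMBG row of Table GPGI.6.2, replace the bare reference to 6.12.1.2 with an explicit rule:

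- Efficacy estimand, EAS.
- Missing Week-40 SMBG multiply imputed within treatment arm, assuming missing at random, from baseline SMBG and on-drug, pre-rescue HbA1c and FSG, plus the last on-drug 4-point daily mean if it is in the database.
- The ANCOVA already described in the row, with results combined by Rubin's rules.
- A supportive ANCOVA on the FAS, labelled treatment-regimen, following the pattern of SAP 6.14. Rescued patients continue their visits, so their Week-40 profiles should exist.

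Imputing from on-drug data has a precedent in SAP 6.12.2.2, which does so for binary endpoints under the efficacy estimand. It reduces the bias but does not eliminate it, particularly for rescue after Week 24, and the report should say so.

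For lipids, state EAS without imputation, as Protocol 10.3.3.3 requires for exploratory endpoints, and add the supportive FAS analysis.

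The cost is a few lines of SAP text and one imputation step on data already scheduled for collection. The downside is reliance on a stated imputation model and slightly more analysis work.

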6.13. Safety Analyses

Unless specified otherwise, safety assessments will be based on the SS (see [Table GPGI.6.1](#)). All events that occur between the date of first dose of study drug to the date of the patient's safety follow-up visit or the patient's end of study participation will be included. For assessing the benefit risk profile through 40 weeks, selected safety analyses will be conducted by utilizing safety data from first dose through the date of the 40-week visit. Some safety analyses may be conducted after excluding data after initiation of new antihyperglycemic therapy. For rare events (<10 patients have the events), summary tables may not be generated, and individual patient level data will be listed.

Unless specified otherwise, comparisons of tirzepatide doses to placebo will be performed.

For selected continuous safety parameters, differences among treatment mean changes from baseline at scheduled visits will be assessed via an MMRM using REML. The model will include treatment, visit, treatment-by-visit interaction, country/pooled country, baseline HbA1c ($\leq 8.0\%$, $> 8.0\%$ [≤ 64 , > 64 mmol/mol]), and baseline metformin use (Yes/No) as fixed effects, and baseline value of the safety parameter as a covariate. To model the covariance structure within patients, the unstructured covariance matrix will be used. If this model fails to converge, the covariance structures specified in [Section 6.12.1.1](#) will be tested in order.

For selected continuous safety parameters only assessed at baseline and primary endpoint, differences among treatment mean changes from baseline in continuous safety parameters at primary endpoint will be assessed via an ANCOVA model. The model will include treatment, country/pooled country, baseline HbA1c ($\leq 8.0\%$, $> 8.0\%$ [≤ 64 , > 64 mmol/mol]), and baseline metformin use (Yes/No) as fixed effects, and baseline value of the safety parameter as a covariate.

For selected safety parameters, time-to-first-event analysis via the Cox proportional hazards model may be conducted. For patients experiencing the event, "time-to-first-event" will be the time (in weeks) from first dose to first occurrence of the event. For patients without the event, "time-to-event" will be censored at end of study participation (study discontinuation, safety follow-up visit, or date of death).

Where specified, the rate of events will be analyzed using a generalized linear mixed-effects model assuming the number of events follow a negative binomial distribution and including treatment as a fixed effect. The logarithm of years in specified time interval will be adjusted as an offset to account for possible unequal treatment duration in specified time interval between patients.

